11.1.2 Progression-free Survival

Progression free survival is the time in days from the first dose of INXN-1001 to the first assessment on which the overall response is reported as disease progression or death due to any cause (whichever is first) + 1 day. Patients withdrawing from the study will be censored at their last non-progressive disease response assessment. If a patient does not have a disease response assessment, the patient will be censored on the date of the first treatment as described above.

Progression-free survival and censoring information will be listed.

PFS times will be summarized using Kaplan-Meier methods. The median, 25th and 75th percentiles will be calculated. Kaplan-Meier plots will not be presented.

11.1.3 Duration of Response

Duration of response will not be calculated.

11.1.4 Immune-Related Response Criteria

Immune-related responses will not be determined.

For ease of use the derived efficacy information will be presented as follows: date of first dose, date of progression, date of death, date of discontinuation, PFS, objective response (yes or no) and best overall response (PD, SD, PR, CR, Unevaluable).

11.2 Pharmacodynamic Endpoints

11.2.1 Immunologic and Biological Response Markers

Immunologic and biological response marker data will be listed only.

11.3 Pharmacokinetic Assessment

PK sample timings will be listed by patient. ZIOPHARM will perform the PK analysis.

12.0 Safety Endpoints

Safety will be assessed from records of AEs, laboratory values (clinical chemistry, hematology and urinalysis), vital signs, 12-Lead electrocardiogram (ECG) and results of physical examination. Severity of adverse events as determined by NCI Common Terminology Criteria for Adverse Events (CTCAE) v4.03.

All safety analyses will be conducted on the SAF population.

12.1 Treatment Exposure

Details of study drug administration including injection of INXN-2001 on Day 1 of each cycle and oral doses of INXN-1001 throughout the study including time on treatment (days) will be listed. Details of planned and actual dosing at each cycle and overall will be listed.

Actual dose of INXN-2001 at each cycle will be calculated as follows:

$$((\text{Number of capsules dispensed} - \text{Number of capsules returned}) \times \text{Strength of capsules}) + \text{Day 1 dose}$$

The strength of capsule prescribed at each dose cohort is as follows in Table 3.

Table 3: Capsule Strength per Dose Cohort

| Dose Cohort | Strength of Capsule |
|-------------|---------------------|
| 5mg | 5mg |
| 20mg | 10mg |
| 80mg | 20mg |
| 120mg | 20mg |
| 160mg | 20mg |

Compliance with the planned dosing regimen will be measured as follows:

Percentage compliance = (Actual dose of INXN-2001 taken)*100
 (Scheduled dose of INXN-2001 to be received)

For scheduled dose regimens of QOD, the dose is administered over a 14 day period, therefore all subjects are scheduled to receive 7 doses within a cycle of treatment.

In instances where subjects receive multiple cycles within a dose group, percentage compliance will be calculated for the entire duration of treatment.

The number of cycles started, total time on treatment, total dose of INXN-2001 taken and percentage compliance will be summarized.

Time on treatment (days) = Last dose date – first dose date +1

Percentage compliance will be presented in the categories: ≤ 80%, 81 – 90%, and 91 – 100%.

The following treatment exposure details will also be listed: date of first dose, number of cycles started, number of cycles completed, total dose of INXN-2001 taken, percentage compliance, reason for discontinuation or ongoing, time on treatment, whether the subject experienced a DLT.

12.2 Adverse Events

Adverse events will be coded according to MedDRA dictionary version 10.

Symptoms and signs of exacerbation or worsening of the patient's primary disease will be captured as AEs.

A treatment emergent adverse event (TEAE) is defined as an AE occurring during or after administration of first dose of study drug, or any event after the first dose of study drug considered study drug-related regardless of event start date, or any worsening in intensity or event considered drug related by the investigator of a pre-existing medical condition/AE with onset after the start of study drug, and until Post-Treatment Safety Assessment visit (28 days after the last INXN-1001 dose per patient). AEs with unknown start date/time will be assumed to be treatment-emergent

unless the end date/time is known to be before start of study drug. AEs with onset after the completion of screening but prior to the start of study drug will be considered non-treatment emergent.

An overall AE summary will be presented for all AEs and the pre-defined subsets of events below:

- Any AEs
- Any TEAE events
- Any drug-related AEs
- Any CTC Grade 3 or greater AEs
- Any CTC Grade 3 or greater drug-related AEs
- Any AEs leading to death
- Any drug-related AEs leading to death
- Any serious AEs (SAEs)
- Any drug-related serious AEs
- Any AEs leading to discontinuation
- Any drug-related AEs leading to discontinuation
- Any dose limiting toxicities

Related is defined as 'possibly related' or 'related' to treatment in the opinion of the investigator.

Both number of events and number of patients will be tabulated. For patients, percentages will be calculated from the total number of patients per INXN-1001 dose cohort in each phase and group (for phase II only).

Summaries of TEAEs, drug-related adverse events, SAEs, drug-related SAEs, AEs with CTC grade ≥ 3 , drug-related AEs with CTC grade ≥ 3 and AEs leading to discontinuation will be tabulated by MedDRA System Organ Class (SOC) and specific AE preferred Term (PT) sorted by decreasing frequency within SOC. Both number of events and number of patients will be tabulated. For patients, percentages will be calculated from the total number of patients per INXN-1001 dose group.

All AEs, TEAEs, SAEs, drug-related adverse events, adverse events leading to discontinuation of study medication and adverse events leading to death will be listed.

Details of injection reactions including injection site reaction, start/stop date/time, outcome, severity, relation to study drug, treatment required details, injection lesion, whether or not a DLT and seriousness will be listed.

Summaries of injection reactions will be tabulated by type, type by severity and type by relationship to study drug and will be presented by phase only. Relationship to study drug refers to either drug.

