6.2.4 Definition and Management of Dose-Limiting Toxicity (DLT)

Dose-limiting toxicity (DLT) is defined as:

- Any injection site reaction that includes ulceration, necrosis, severe tissue damage or where operative intervention is required.
- Any local or systemic injection reaction that has life-threatening consequences, requires urgent intervention or results in death.

- Any study drug-related \geq Grade 3 adverse event, except nausea and/or vomiting in subjects who did not receive optimal treatment with anti-emetics.

Phase I and Phase II, Group 1: If DLTs have been observed in >1 of the 3-6 subjects in a cohort during the first treatment cycle, the MTD will have been exceeded and further use of that dose will be discontinued in all subjects, and the next lower dose cohort will be assessed as to whether it meets the definition of the MTD.

Phase II, Group 2: If an adverse event that meets the Phase I DLT definition is observed in >1 of the 3-6 subjects in Group 2 during the first treatment cycle, the SRC will convene to discuss reduction in dose and/or change to posology and the cohort will be expanded by 3 subjects. The recommended Phase II dose will be the dosage and posology where ≤ 1 of 3 to 6 subjects experiences an adverse event as described in the definition of DLT.

The Medical Monitor should be immediately notified of any potential DLT. Subjects will be withdrawn from study treatment if they experience an injection site reaction that meets DLT criteria or other Grade 3 toxicity related to study drug that, upon review of the SRC, is deemed to be a DLT. If, however, the subject has experienced a substantial benefit from treatment and the SRC recommends continuation on the study, re-exposure to the experimental treatment may proceed at a lower dose of INXN-1001 on a case by case basis. Any subject who experiences a Grade 4 toxicity related to study treatment will be withdrawn from study.

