8.2.6 Retreatment Criteria, Dose Delays and Modifications

Subjects may receive up to 6 cycles of study drug treatment. In order to receive each repeat treatment cycle, all treatment-related adverse events must have resolved to Grade 1 or baseline and the following laboratory criteria must be met:

- Hemoglobin ≥ 9 g/L
- Lymphocytes $> 700/\text{mm}^3$
- Neutrophils $\geq 1,500/\text{mm}^3$
- Platelets $\geq 100,000/\text{mm}^3$
- Serum creatinine $\leq 1.5 \times \text{ULN}$
- AST and ALT $\leq 2.5 \times \text{ULN}$. For subjects with documented liver metastases, ALT and AST $\leq 5 \times \text{ULN}$
- Total bilirubin $< 1.5 \times \text{ULN}$
- INR and PTT $< 1.5 \times \text{ULN}$, if not therapeutically anticoagulated.

Clinical laboratory tests drawn for analysis on Day 15 of each cycle may be used for determining if the retreatment criteria have been met, and must be reviewed by the investigator or designee prior to the next cycle of study drug administration. Treatment delays to allow for recovery to acceptable levels are allowed at weekly intervals up to a maximum of 4 weeks. In the event that a treatment-related dose delay is necessary, then the next cycle of study treatment will be administered at the next lower INXN-1001 dose level. Subjects in the first dose cohort who do not meet the retreatment criteria will be discontinued from study treatment (ie, no dose reductions are permitted).

Subjects who experience a DLT will be managed as described in [Section 6.2.4](#). Subjects who experience an injection site reaction should be managed as described in [Section 8.2.7](#).

Subjects who experience a treatment-related Grade 3 adverse event, other than nausea and/or vomiting in the absence of optimal treatment with anti-emetics, will be discontinued from study treatment. If, however, the subject has experienced a substantial benefit from treatment and the SRC recommends continuation on the study, re-exposure to the experimental treatment may proceed on a case by case basis.

Subjects who experienced a Grade 4 treatment-related adverse event at any time during study treatment must be discontinued from study treatment.

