9.2.2 Determination of Severity

The severity of AEs will be assessed according to the NCI CTCAE, v. 4.03. If the AE is not defined in the NCI CTCAE, v. 4.03, the Investigator will determine the severity of an AE based on the following definitions:

- **Mild (Grade 1)**: The AE is noticeable to the patient, but does not interfere with routine activity. The AE does not require discontinuing administration or reducing the dose of the study drug.
- **Moderate (Grade 2)**: The AE interferes with routine activity, but responds to symptomatic therapy or rest. The AE may require reducing the dose, but not

discontinuing administration of the study drug.

- Severe (Grade 3): The AE significantly limits the patient's ability to perform routine activities despite symptomatic therapy. In addition, the AE leads to discontinuing administration or reducing the dose of the study drug.
- Life Threatening (Grade 4): The AE requires discontinuing administration of the study drug. The patient is at immediate risk of death.
- Death (Grade 5): The patient dies as a direct result of the complication or condition

Adverse events should be reported using the maximum intensity of the event (eg, if a subject reported nausea lasting 3 days, one start date and stop date should be recorded along with the maximum intensity experienced for that event over that 3 day timeframe).

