9.3 DOCUMENTING ADVERSE EVENTS (AES)

All AEs (including SAEs) are to be accurately recorded on the Adverse Event page of the patient's eCRF from the time the patient signs the informed consent until the post-treatment safety visit. Each event will be assessed for serious criteria, severity, and causality (See "Causality Assessments"). The date of onset, as well as the duration of the event will be recorded. In addition, treatments provided to the patient, actions taken with the study drugs, and the outcome of the AE will also be noted.

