10.3.2 Safety Analyses

The Safety Population will be used for the analyses of safety data based on the dose of INXN-1001 received.

Safety evaluations will be based on the incidence, intensity, and type of AEs and SAEs. Clinically significant changes in the subjects' physical examinations, vital signs, and ECG evaluations, and clinical manifestations relevant to abnormal laboratory values will be captured as AEs. Safety will also be assessed based on medical history and prior/concomitant medications.

AEs will be coded using the Medical Dictionary for Regulatory Activities (MedDRA[®]) for the purpose of summarization. All AEs occurring during the study will be included in by-subject data listings. Treatment-emergent events will be tabulated. 'Treatment-emergent' is defined as any AE that occurs during or after administration of the first dose of study drug through the Post-Treatment Safety Assessment visit (28 days after the last INXN-1001 dose); any event after the first dose of study drug that is considered study drug-related regardless of the start date of the event; or any event that is present at baseline that worsens in intensity or is subsequently considered to be drug related by the investigator. Deaths, SAEs, and AEs resulting in study discontinuation will be listed.

Safety variables will be tabulated and presented by dose cohort. Exposure to study drug and reasons for discontinuation of study treatment will be tabulated.

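### SAP 12.2 contradicts its own TEAE definition for adverse events that start between the end of screening and first dose, and the recorded data as described cannot show later worsening

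*SAP*

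**What the plan says.** SAP 12.2 gives three routes to TEAE status: onset during or after the first dose; relatedness to study drug after first dose, irrespective of start date; and "any worsening in intensity or event considered drug related by the investigator of a pre-existing medical condition/AE with onset after the start of study drug". I read the onset phrase in that last route as dating the worsening, since a pre-existing event cannot itself begin after study drug. The final sentence of the paragraph then states that "AEs with onset after the completion of screening but prior to the start of study drug will be considered non-treatment emergent". It gives no exception, no order of precedence and no definition of when screening is complete.

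Protocol 10.3.2 also counts as treatment-emergent "any event that is present at baseline that worsens in intensity or is subsequently considered to be drug related by the investigator". It has no exclusion based on onset alone. SAP 14, which lists the changes from the protocol's planned analysis, does not mention the TEAE definition.

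On recording, protocol 9.2.2 asks for the maximum intensity of an event and illustrates this with nausea lasting 3 days, for which "one start date and stop date should be recorded along with the maximum intensity experienced for that event". Protocol 9.3 adds: "The date of onset, as well as the duration of the event will be recorded". Neither section says that a rise in grade opens a new record or is dated. AEs go on the AE CRF from informed consent (protocol 8.4.2.6).

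**The concern.** Safety and tolerability are the primary objective, and TEAE status decides which events enter several of the main safety outputs. There are two separate problems.

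- **Rule.** A programmer given an AE that starts after screening but before dosing, and then worsens or is judged related, meets two instructions in one paragraph that give opposite answers. Following the last sentence removes from the TEAE tables an event that protocol 10.3.2 says belongs there.
- **Data.** Suppose the definition is given precedence. The worsening route still needs the grade at first dose and some evidence of a later rise. A record holding one start date and one maximum grade supplies neither.

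**Working it through.** The plan states no figure on this point and is descriptive throughout (SAP 9.0), so there is nothing to reproduce. The check is a comparison of rules followed by simple percentages.

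**Step 1: cross the two rules.** Take four onset windows (before consent; consent to end of screening; end of screening to first dose; after first dose), each with worsened yes/no and related yes/no. That is 4 × 2 × 2 = 16 cells.

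- Definition: TEAE if onset is after first dose, or the event worsened after it, or it is judged related.
- Closing sentence: not a TEAE if onset lies between the end of screening and first dose.

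The rules conflict in 3 of the 16 cells, all in the third window:

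| Worsened | Related | Definition | Closing sentence | Result |
|---|---|---|---|---|
| No | No | Not TEAE | Not TEAE | Agree |
| No | Yes | TEAE | Not TEAE | Conflict |
| Yes | No | TEAE | Not TEAE | Conflict |
| Yes | Yes | TEAE | Not TEAE | Conflict |

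In the other 12 cells the closing sentence does not apply.

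**Step 2: what one record can show.** Take an unrelated AE stored with a pre-dose start and maximum Grade 2. It may have been Grade 2 throughout (not a TEAE), or Grade 1 at first dose and Grade 2 later (a TEAE). Both histories give the same record.

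- The gap covers unrelated AEs that start anywhere between consent and first dose.
- Related events are classified through relatedness, provided the closing sentence is not applied.
- Symptoms in the medical history are protected, because protocol 9.1 asks for a baseline grade so that worsening is recognised as an AE.
- Events with onset after first dose are TEAEs in every cell.

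**Step 3: outputs reached (SAP 15.1 and 15.3).**

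- Restricted to TEAEs: the TEAE row of Table 14.3.2.1, Tables 14.3.2.3 and 14.3.2.4, and Listings 16.2.7.2 to 16.2.7.6.
- Not restricted by title: Table 14.3.2.2 (all AEs), Tables 14.3.2.5 and 14.3.2.6 (SAEs), Tables 14.3.2.7 and 14.3.2.8 (Grade 3 or greater), and Listing 16.2.7.1.
- A related, non-serious Grade 1 or 2 event removed by the closing sentence would appear in no drug-related table by system organ class and preferred term. It would remain in Table 14.3.2.2.

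**Step 4: size.** SAP 1.0 gives cohorts of 3, 3, 3 and 4 in Phase I (total 13) and 4, 4, 3 and 2 in Phase II (total 13), so 26 patients. One patient changes a row by 100/n points:

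- n = 4: 100/4 = 25.0
- n = 3: 100/3 = 33.3
- n = 2: 100/2 = 50.0
- Overall column for a phase, n = 13: 100/13 = 7.7

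**The case against.** The strongest reply is that the intention is clear and the exposure small. Both documents expressly count worsening as treatment-emergent, so a sensible programmer would let the definition prevail. The schedule in protocol Table 2 places Day -28 to -7 and Day -6 to -2 under screening. On that reading the closing sentence covers only about Day -1 to first dose. The one-record instruction is illustrated by a single 3-day example, protocol 9.1 says that worsening of a preexisting condition is itself an AE, and the CRF and its completion instructions are not available. A second record or a date of grade change may therefore exist.

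Most of this limits the point without removing it. Intention does not settle precedence when the later sentence is specific and has no exception. The narrow window depends on a term the SAP leaves undefined. The unseen CRF makes the data gap conditional, and it is stated that way here.

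Three stronger readings are tempting, and the documents do not support them:

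- **All worsening after first dose is lost.** It is not. The explicit worsening routes in SAP 12.2 and protocol 10.3.2 stand outside the one conflicting window.
- **Biopsy-site events are reclassified.** An event at Day -4, after the punch biopsy, falls within screening as the schedule labels it, so the closing sentence probably does not reach it. If it is judged possibly related, the SAP counts it as related and makes it a TEAE whatever its start date.
- **A later-cycle Grade 3 becomes a false Cycle 1 DLT.** Retreatment requires that "all treatment-related adverse events must have resolved to Grade 1 or baseline", so a Grade 1 event can run across cycles, and one record would carry its Cycle 1 start date. But nothing derives DLT status or cycle from an AE start date. Potential DLTs are notified to the Medical Monitor at once and reviewed by the Safety Review Committee (protocol 6.2.4). Phase I escalation is reviewed once the third subject completes Cycle 1 (protocol Appendix 5), later events are considered separately (6.2.5, 6.2.7), and no SAP table is by cycle.

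**Conclusion.** The point holds as an internal contradiction in SAP 12.2, confined to AEs with onset after screening and before study drug, together with an undeclared departure from protocol 10.3.2. A second, conditional gap concerns unrelated AEs opened on the AE CRF before first dose: their later worsening cannot be derived from the data as the protocol describes them.

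The row shifts of 25, 33.3 or 50 points by cohort, or 7.7 points Overall, apply only to a preferred-term row in which that patient has no other event. They are sensitivities for one patient; the documents do not show whether any such patient exists. The conclusion assumes that table titles describe their content and that the CRF does not record grade changes. If the CRF does record them, the data gap closes and only the wording conflict remains. Nothing here calls the dose decisions into question.

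**What to change.** 1. **SAP 12.2.** Add to the closing sentence: *unless the event worsened in intensity, or was considered drug-related, after the first dose of study drug*.
2. **SAP 12.2.** Define the completion of screening by a date that exists in the database.
3. **Data.** For AEs with onset before first dose that were still ongoing at first dose, query the grade at first dose and the date of any later increase. If the CRF already holds these, use them.

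The cost is one clause, one definition and a limited set of queries among 26 patients; TEAE counts may rise slightly. A prospective change to AE recording would come too late, since SAP 1.0 already reports the treated numbers. Counting every ongoing pre-dose AE as treatment-emergent by default is not advised, because protocol 10.3.2 requires worsening or relatedness.

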6.2 STUDY DESIGN AND DOSE ESCALATION PROCEDURE

6.2.1 Overall Study Design

This is a single-arm, open label, Phase I/II dose escalation study of intratumoral injections of INXN-2001 and oral INXN-1001 in subjects with unresectable Stage III or IV melanoma.

Phase I: Four sequential dose escalation cohorts of INXN-1001 in combination with a fixed dose of INXN-2001 are planned. Subject enrollment and dose escalation will proceed according to a standard 3+3 design. Each subject will be treated for up to 6 treatment cycles, each 21 days in duration. Previously enrolled subjects received 3 cycles under former versions of this protocol. There will be at least 7 days between the initiation of treatment for the sentinel (first) subject and additional subjects in all cohorts during the dose escalation stage of the study. In each cycle, subjects will be treated with one intratumoral injection of INXN-2001 in combination with 7 oral daily doses of INXN-1001. No intrasubject dose escalation will be allowed.

Phase II: Approximately 15 subjects will be enrolled in Phase II at or below the MTD. For Group 1, in each of six 21-day cycles, the subjects will receive one intratumoral injection of INXN-2001 in combination with 7 oral daily doses of INXN-1001. For Group 2, in each of six 28-day cycles, the subjects will receive one intratumoral injection of INXN-2001 in combination with 7 oral doses of INXN-1001 administered every other day for 14 days.

Safety and tolerability will be assessed by the incidence and severity of adverse events as determined by NCI Common Terminology Criteria for Adverse Events (CTCAE) v4.03. A SRC comprised of the Medical Monitor, Principal Investigators, and sponsor representatives, will be convened to review safety information and to decide upon dose escalation and further subject enrollment.

The anti-tumor activity of study treatment will be assessed according to RECIST v1.1 guidelines. Additional assessment of anti-tumor activity will be explored based on total measurable tumor burden.³⁹ ([Appendix 4](#))

Immunological and biological markers of response will include examinations of tumor biopsy samples, cytokine levels, PBMCs and antibody response to INXN-2001.

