1. Tabular Summary of Revisions Implemented in the Amended Protocol

Section in Amended Protocol	Original Text/Section	Revised Text/Section	Rationale for Change
Throughout Protocol	Not applicable. Subjects may receive up to 3 cycles of therapy	A few minor grammatical edits, clarifications, and other adjustments have been implemented throughout the protocol and will not be individually listed in this summary, but are indicated in the "track changes" version of the study protocol. Subjects may receive up to 6 cycles of therapy	Improve readability. Increase number of cycles of therapy that may be administered.
Title Page, Page Headings and Footers.	Amendment 3: 19 April 2012	Amendment 4: 13 July 2012	Update to current protocol version and date of amendment.
Title Page			Update Sponsor contact information.
Section 3 Protocol Synopsis; No. of Subjects	30 subjects (6 subjects per dose level cohort and up to 6 additional subjects enrolled at a single dose level at or below the MTD), exclusive of replacement subjects or the addition of intermediate dose level cohorts, if any.	Approximately 30 subjects (3 subjects per dose level cohort and approximately 15 subjects enrolled in an expansion cohort at a single dose level at or below the MTD), exclusive of replacement subjects or the addition of intermediate dose level cohorts, if any.	Describe the modification to the study design to include an expansion cohort.
Section 3 Study Design; Number of Centers	Multi-center (approximately 5 to 10 centers)	Multi-center (approximately 8 to 12 centers)	Revise number of potential sites.
Section 3 Protocol Synopsis; Study Design	Four sequential dose escalation cohorts of INXN-1001 in combination with a fixed dose of INXN-2001 are planned (Table 1). Subject enrollment and dose escalation will proceed according to a standard 3+3 design. Each subject will be treated for up to three treatment cycles, each of 21 days in	Each subject will be treated for up to 6 treatment cycles, each of 21 days in duration. Previously enrolled subjects received 3 cycles under former versions of this protocol. There will be at least 7 days between the initiations of treatment for the sentinel (first) subject and additional subjects in all cohorts	Increase the number of treatment cycles from 3 to 6. Describe the modification to

Section in Amended Protocol	Original Text/Section	Revised Text/Section	Rationale for Change

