4.2 Overall Study Design

This was a single-arm, open label, Phase I/II dose escalation study of intratumoral injections of INXN-2001 and oral INXN-1001 in patients with unresectable Stage III or IV melanoma.

Approximately 30 patients (3 patients per dose level cohort) in Phase I and approximately 15 patients were to be enrolled in Phase II at a single dose level at or below the Maximum Tolerated Dose (MTD)).

Concurrent INXN-2001 and INXN-1001 dosing will be referred to as "study treatment" throughout this SAP.

This study is multi-center (approximately 8 to 12 centers).

Phase I

Phase I comprised of four planned sequential dose escalation cohorts of INXN-1001 in combination with a fixed dose of INXN-2001. Patient enrollment and dose escalation was to proceed according to a standard 3+3 design. Each patient was to be treated for up to 6 treatment cycles, each of 21 days in duration. In each cycle, patients were to be treated with one intratumoral injection of INXN-2001 in combination with 7 oral daily doses of INXN-1001 (Table 1).

Table 1: Study Design

| Study Part | Cohorts | Dose Regimen |
|------------|-----------------|---|
| Phase I | Dose Escalation | INXN-2001: [REDACTED] INXN-1001: 5, 20, 100, 160 mg |
| Phase II | Group 1 | INXN-2001: [REDACTED] INXN-1001: 160 mg daily for 7 consecutive days; 21-day cycle |
| | Group 2 | INXN-2001: [REDACTED] INXN-1001: 160 mg every other day for 14 days; 28-day cycle |

This study was to explore four INXN-1001 dose cohorts of 5 mg, 20 mg, 100 mg and 160 mg daily.

Phase II

Approximately 15 patients were to be enrolled in Phase II at or below the MTD. Phase II of the study was to include two groups of patients. Patients enrolled in Phase II of the study under Amendment 6 or prior were to be enrolled into Group 1; patients enrolled under Amendment 7 or later were to be enrolled into Group 2.

For Group 1, in each of six 21-day cycles, the patients were to receive one intratumoral injection of INXN-2001 in combination with oral daily doses of INXN-1001 given at 160 mg for 7 consecutive days at the beginning of the 21-day cycle.

For Group 2, in each of six 28-day cycles, the patients were to receive one intratumoral injection of INXN-2001 in combination with oral doses of INXN-1001 given at 160 mg administered every other day for 14 days at the beginning of the 28-day cycle.

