Full details of the study design can be found in the protocol. Following changes to patient enrollment, the final study is shown in Table 2.

Table 2: Final Study Design

| Study Part | Cohorts | Dose Regimen |
|------------|-----------------|---|
| Phase I | Dose Escalation | INXXN-2001: [REDACTED] INXXN-1001: 5, 20, 100, 160 mg |
| Phase II | Group 1 | INXXN-2001: [REDACTED] INXXN-1001: 160 mg daily for 7 consecutive days; 21-day cycle |
| | Group 2 | INXXN-2001: [REDACTED] INXXN-1001: 160 mg every other day for 14 days; 28-day cycle 120 mg every other day for 14 days; 28-day cycle 80 mg every other day for 14 days; 28-day cycle |

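### Crude adverse event percentages by dose cohort are taken over observation windows of unequal length (3-cycle against 6-cycle caps), so differences across Phase I doses and between phases may partly reflect observation time

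*SAP*

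**What the plan says.** **Summary measure.** SAP 12.2 tabulates numbers of events and numbers of patients. For patients, "percentages will be calculated from the total number of patients per INXN-1001 dose cohort in each phase and group". It specifies no per-cycle rate, person-time rate or common observation window. A treatment-emergent event counts from first dose until the Post-Treatment Safety Assessment, placed 28 days beyond that patient's own final INXN-1001 dose.

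**Number of cycles.** Protocol 6.2.1 says of Phase I: "Each subject will be treated for up to 6 treatment cycles, each 21 days in duration". It then adds: "Previously enrolled subjects received 3 cycles under former versions of this protocol". The Amendment 4 summary appended to the protocol gives the reason for the change: "Increase number of cycles of therapy that may be administered". The same amendment created what is now Phase II: "approximately 15 subjects enrolled in an expansion cohort at a single dose level at or below the MTD".

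**Cycle length.** Phase I and Phase II Group 1 use 21-day cycles. SAP 4.2 says: "For Group 2, in each of six 28-day cycles, the patients were to receive one intratumoral injection". Table 2 of that section carries the same cycle length to the reduced doses, for example "80 mg every other day for 14 days; 28-day cycle".

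**What the SAP leaves out.** SAP 4.2 describes Phase I only as up to 6 cycles. Neither that section nor SAP 14 mentions the 3-cycle subjects.

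**The concern.** Safety is the primary objective, and informing the choice of INXN-1001 dose and regimen is a secondary one. Readers will compare the adverse event columns from dose to dose and from phase to phase. A patient followed for up to 6 cycles has more time to record a first event than one limited to 3, even if both doses are equally toxic.

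The cap is linked to dose through calendar time. Protocol Appendix 5 starts escalation at the lowest dose and holds the next cohort until the third subject has finished Cycle 1. The subjects treated under the 3-cycle versions are therefore those at the lowest dose or doses. All Phase II subjects fall under the 6-cycle limit, because the expansion cohort arrived in the amendment that raised it. The Phase I Overall column (SAP 9.0) and the injection-reaction tables, which SAP 12.2 presents by phase only, may pool both caps.

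**Working it through.** **Denominators.** From SAP 1.0, Phase I has 3 + 3 + 3 + 4 = 13 and Phase II has 4 + 4 + 3 + 2 = 13. Both match SAP 6.1. The documents state no adverse event rate, so every risk below is an assumption.

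**Maximum treatment-emergent window, without dose delays.** Window = (cycles − 1) × cycle length + last INXN-1001 dosing day of the final cycle + 28. The last dosing day is Day 7 for daily dosing and Day 13 for every-other-day dosing.

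| Schedule | Calculation | Days | Ratio to 77 |
|---|---|---|---|
| 3 x 21, daily | 2×21 + 7 + 28 | 77 | 1 |
| 6 x 21, daily | 5×21 + 7 + 28 | 140 | 1.82 |
| 6 x 28, every other day | 5×28 + 13 + 28 | 181 | 2.35 |

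**Equal toxicity, full exposure, constant per-cycle risk p (assumed).** Cumulative incidence = 1 − (1 − p)^cycles.

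| p | 3 cycles | 6 cycles | Gap (points) |
|---|---|---|---|
| 5% | 14.3% | 26.5% | 12.2 |
| 10% | 27.1% | 46.9% | 19.8 |
| 20% | 48.8% | 73.8% | 25.0 |

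Under the same assumptions, expected event counts double (6/3).

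**Front-loaded toxicity.** Let the hazard from Cycle 3 onward be r times that in Cycles 1-2, and fix the 3-cycle risk at 50%. The 6-cycle risk is then 1 − 0.5^((2 + 4r)/(2 + r)).

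| r | 0 | 0.10 | 0.25 | 0.50 | 1 |
|---|---|---|---|---|---|
| 6-cycle risk | 50% | 54.7% | 60.3% | 67.0% | 75.0% |

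**Early discontinuation.** With a fraction q leaving per cycle (assumed), mean cycles = Σ(1 − q)^k for k = 0 to cap − 1.

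| q | 3-cycle cap | 6-cycle cap | Ratio |
|---|---|---|---|
| 0 | 3 | 6 | 2.00 |
| 10% | 2.71 | 4.69 | 1.73 |
| 20% | 2.44 | 3.69 | 1.51 |
| 30% | 2.19 | 2.94 | 1.34 |
| 40% | 1.96 | 2.38 | 1.22 |

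**Precision.** The exact 95% interval is 0.8% to 90.6% for 1 of 3 patients and 19.4% to 99.4% for 3 of 4.

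**The case against.** The strongest reply is that the extra time may hold few events. Protocol Appendix 3 says most toxicity has been seen from the first injection through Cycle 2, a period that both caps cover. If none arises later, the gap is zero. Related Grade 3 events (with exceptions) and Grade 4 events end treatment under Protocol 6.2.4 and 8.2.6, and Protocol 7.3 allows withdrawal for clinically significant progression. Higher doses could therefore have had shorter actual exposure, which would shrink or reverse the effect. This stands, and it rules out any claim about direction. It does not remove the point. Appendix 3 gives no figures, and SAP 12.2 also counts signs of worsening melanoma as adverse events, which need not be front-loaded.

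Second, the SAP is purely descriptive, and cohorts of 2 to 4 patients move by 25 to 50 points per patient, so the illustrated gaps amount to one patient at most. This also stands: no adjustment will make a trend precise. Descriptive columns should still cover comparable windows.

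Third, exposure is already reported. SAP 12.1 summarises cycles started and time on treatment, and SAP 10.1 lists the amendment each patient was recruited under. These outputs are separate from the adverse event tables, and a marginal exposure summary cannot show which events began after Cycle 3.

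Fourth, dose decisions rest on first-cycle DLTs, which the cap cannot affect. That is correct, although Protocol 6.2.5 and 6.2.7 let the SRC reconsider the MTD on later events.

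**Conclusion.** The crude percentages and event counts in SAP 12.2 may confound dose with observation time across Phase I doses and between phases. The potential window differs 1.82-fold through the cap alone, and 2.35-fold when Group 2's longer cycles are added. At equal toxicity the 3 against 6 cycle gap runs from near zero, if toxicity is confined to Cycles 1-2, to about 12 to 25 points at 5% to 20% constant risk per cycle with full exposure.

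A reader might infer more than the documents support:

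- **That part of any dose-toxicity trend is only longer exposure, biased against later cohorts.** This needs patients who actually went beyond 3 cycles and first events arising after Cycle 3. The documents show neither.
- **That the cap maps cleanly onto cohorts.** Neither document states the switch point or how many patients had each cap, and one cohort may hold both.
- **That treatment time differs as 63 days (3 x 21) against 168 (6 x 28).** That contrast mixes cap with cycle length and omits the 28-day tail. The cap alone gives 63 against 126 (6 x 21).
- **That Phase II comparisons share the problem.** All Phase II subjects had the 6-cycle limit, and the 160, 120 and 80 mg every-other-day cohorts also share a cycle length. Groups 1 and 2 differ only through 21- against 28-day cycles (140 against 181 days).

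**What to change.** Keep the crude tables. For TEAEs, drug-related TEAEs and Grade ≥3 adverse events, add incidence restricted to Cycle 1 and to Cycles 1-3, and print each cohort's cycle cap and cycles received beside them. Close the Cycles 1-3 window at the same nominal point for everyone, so that the post-treatment tail of a 3-cycle patient is not counted against a patient who went on to Cycle 4. This removes the gap due to the cap by construction. Group 2 would still differ in length (3 x 28 = 84 days against 3 x 21 = 63), which a footnote should say.

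If a rate is shown, give it per patient-time and only as a supplement, with a note that toxicity is front-loaded. Such a rate dilutes toxicity in patients with more cycles, and a rate per patient-cycle would also treat 21- and 28-day cycles as equal.

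The cost is a few extra columns from adverse event dates, dosing dates and amendment of recruitment, all of which the SAP already lists. Cohorts of 2 to 4 patients remain imprecise.
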